8.3.2. Reporting

Every SAE, regardless of suspected causality (eg, relationship to study drug(s) or study procedure or disease progression), occurring after the subject has signed the ICF through the last study visit (or 90 days after the last dose of study drug, whichever is later) must be reported to the sponsor (or designee) within 24 hours of learning of its occurrence, unless otherwise specified by the Protocol. Any SAEs occurring more than 90 days after the last dose of study drug should be reported to the sponsor or its designee only if the investigator suspects a causal relationship to the study drug.

Information about all SAEs is collected and recorded on the Adverse Event form of the eCRF. The investigator must assess and record the causal relationship of each SAE to the study treatment.

The investigator must also complete the Incyte Serious Adverse Event Report Form, in English, and send the completed and signed form to the sponsor or designee within 24 hours of becoming aware of the SAE. The investigator must provide a causality assessment, that is, assess whether there is at least a reasonable possibility that the SAE is related to the study treatment: suspected (yes) or not suspected (no). Refer to the Incyte Reference Guide for Completing the Serious Adverse Event Report Form.

The contact information of the sponsor's study-specific representatives is listed in the investigator manual provided to each site. The original copy of the SAE Report Form and the confirmation sheet must be kept at the study site.

Investigational site personnel must report any new information regarding the SAE within 24 hours of becoming aware of the information in the same manner that the initial SAE Report Form was sent. Follow-up information is recorded on an amended or new SAE Report Form, with an indication that it is follow-up to the previously reported SAE and the date of the original report. The follow-up report should include information that was not provided on the previous SAE Report Form, such as the outcome of the event (eg, resolved or ongoing), treatment provided, action taken with study drug because of the SAE (eg, dose reduced, interrupted, or discontinued), or subject disposition (eg, continued or withdrew from study participation). Each recurrence, complication, or progression of the original event should be reported as follow-up to that event, regardless of when it occurs.

If the SAE is not documented in the IB for the study drug, or in the US package insert or Summary of Product Characteristics for marketed drugs as appropriate, (new occurrence) and is thought to be related to the sponsor's study drug, the sponsor or its designee may urgently require further information from the investigator for reporting to health authorities. The sponsor or its designee may need to issue an Investigator Notification (IN) to inform all investigators involved in any study with the same drug that this SAE has been reported. Suspected Unexpected Serious Adverse Reactions (SUSARs) will be collected and reported to the competent authorities and relevant ethics committees in accordance with Directive 2001/20/EC, or as per national regulatory requirements in participating countries.

8-4- Adverse Events of Special Interest

Adverse events of special interest include irAEs that are seen with immunotherapy and any other observed autoimmune phenomenon. Guidance for the assessment, diagnosis, and management of irAEs is provided in Section 5.4.1.3. Immune-related AEs will be monitored carefully at each cycle and during the safety follow-up period.

As noted in Section 1.8.1, there is an uncommon risk that epacadostat could cause an increase in serotonin levels in the brain that might trigger SS (Boyer and Shannon 2005) when administered in combination with other serotonergic agents. This syndrome has been most closely associated with use of MAOis, mepelidine, linezolid, or methylene blue; all of these agents are prohibited during the study. Selective serotonin reuptake inhibitors and SNRIs are permitted in the study. Procedures listed in Section 5.4.3 will be implemented if subjects exhibit the signs/symptoms of SS, including tremor, hyporeflexia, spontaneous, ocular, or inducible clonus together with agitation, fever, diaphoresis, or muscle rigidity.

8.5. Emergency Unblinding of Treatment Assignment

Not applicable.

8.6. Pregnancy

Pregnancy, in and of itself, is not regarded as an AE unless there is suspicion that study drug may have interfered with the effectiveness of a contraceptive medication or method. When a pregnancy has been confirmed in a subject during maternal or paternal exposure to study drug, the following procedures should be followed in order to ensure subject safety:

- The study drug must be discontinued immediately (female subjects only; see Section 5.4.1.2 for the maximum permitted duration of study drug interruption).
- The investigator must complete and submit the Incyte Clinical Trial Pregnancy form to the sponsor or its designee within 24 hours of learning of the pregnancy.

Data on fetal outcome and breastfeeding are collected for regulatory reporting and drug safety evaluation. Follow-up should be conducted for each pregnancy to determine outcome, including spontaneous or voluntary termination, details of the birth, and the presence or absence of any birth defects, congenital abnormalities, or maternal and/or newborn complications, by following until the first well-baby visit. Pregnancy should be recorded on a Clinical Trial Pregnancy form and reported by the investigator to the sponsor or its designee. Pregnancy follow-up information should be recorded on the same form and should include an assessment of the possible causal relationship to the sponsor's study drug to any pregnancy outcome, as well as follow-up to the first well-baby visit or the duration specified in local regulations, whichever is later. Refer to the Incyte Reference Guide for Completing the Clinical Trial Pregnancy Form.

Any SAE occurring during pregnancy must be recorded on the SAE report form and submitted to the sponsor or designee.

8.7. Warnings and Precautions

Special warnings or precautions for the study drug, derived from safety information collected by the sponsor or its designee, are presented in the epacadostat Investigator's Brochure (IB). Additional safety information collected between IB updates will be communicated in the form of INs. Any important new safety information should be discussed with the subject during the study, as necessary. If new significant risks are identified, they will be added to the ICF.

8.8. Data Monitoring Committee

Not applicable.

8.9. Product Complaints

The sponsor collects product complaints on study drugs and drug delivery systems used in clinical studies in order to ensure the safety of study participants, monitor quality, and facilitate process and product improvements.

All product complaints associated with material packaged, labeled, and released by the sponsor or its designee will be reported to the sponsor. All product complaints associated with other study material will be reported directly to the respective manufacturer.

The investigator or his/her designee is responsible for reporting a complete description of the product complaint via email or other written communication to the sponsor contact or respective manufacturer as noted in the packaging information. Any AE associated with a product complaint should be reported as described in Section 8.1.2 of this Protocol.

If the investigator is asked to return the product for investigation, he/she will return a copy of the product complaint communication with the product.

9. STATISTICS

9.1. Study Populations

The safety population includes all subjects enrolled in the study who received at least 1 dose of study drug (azacitidine, INCB057643, INCB059872, pembrolizumab, or epacadostat). All safety analyses will be based on the safety population.

The full analysis set includes all subjects enrolled in the study who received at least 1 dose of study drug (azacitidine, INCB057643, INCB059872, pembrolizumab, or epacadostat) and had at least 1 postbaseline assessment or discontinued treatment. All efficacy analyses will be based on the full analysis set.

9.2. Selection of Sample Size

9.2.1. Sample Size in Part 1

9.2.1.1. Dose Escalation

The primary objective of Part 1 of the study is to determine the MTD, maximum tested dose, or PAD of the triplet combination of azacitidine, INCB057643, or INCB059872 with pembrolizumab and epacadostat. The total number of subjects will depend on the number of dose levels tested before the MTD, maximum tested dose, or PAD is established.

A 3 + 3 + 3 dose-escalation design will be used in Part 1. Based on 3 + 3 + 3 design algorithm, 3 to 9 subjects will be enrolled at each dose level. The algorithm of 3+3+3 is detailed in Section 4.1.1. The probability of dose de-escalation from a given dose level for the various DLT rates are provided in Table 55. For example, if the true DLT rate is 20% at a given dose level, there is a 78.4% chance that the dose would be escalated.

Table 55: Probability of Dose De-Escalation for Various Dose-Limiting Toxicity Rates

True DLT Rate	Probability of Dose De-Escalation
20%	21.6%
30%	43.9%
40%	65.0%
50%	81.1%
60%	91.2%

9.2.1.2. Dose Expansion

In addition to the dose-escalation cohorts, dose-expansion cohorts for Treatment Groups B and C in 5 NSCLC subjects who progressed on a PD-1 pathway-targeted agent and 5 MSS CRC subjects will be [REDACTED] at each dose level tested that clears the DLT window for signal detection [REDACTED] analysis to guide an RP2D.

The expansion will include:

1. Safety/efficacy cohorts in NSCLC
 - a. B-1: INCB057643 4 mg QD followed by the pembrolizumab/epacadostat doublet
 - b. B-3: INCB057643 8 mg QD followed by the pembrolizumab/epacadostat doublet
 - c. B-5: INCB057643 12 mg QD followed by the pembrolizumab/epacadostat doublet
 - d. C-1: INCB059872 1 mg QoD followed by the pembrolizumab/epacadostat doublet
 - e. C-3: INCB059872 2 mg QoD followed by the pembrolizumab/epacadostat doublet
 - f. C-5: INCB059872 1 mg QD followed by the pembrolizumab/epacadostat doublet
 - g. C-7: INCB059872 3 mg QoD followed by the pembrolizumab/epacadostat doublet
2. Safety/efficacy cohorts in CRC
 - a. B-2: INCB057643 4 mg QD followed by the pembrolizumab/epacadostat doublet
 - b. B-4: INCB057643 8 mg QD followed by the pembrolizumab/epacadostat doublet
 - c. B-6: INCB057643 12 mg QD followed by the pembrolizumab/epacadostat doublet
 - d. C-2: INCB059872 1 mg QoD followed by the pembrolizumab/epacadostat doublet
 - e. C-4: INCB059872 2 mg QoD followed by the pembrolizumab/epacadostat doublet
 - f. C-6: INCB059872 1 mg QD followed by the pembrolizumab/epacadostat doublet
 - g. C-8: INCB059872 3 mg QoD followed by the pembrolizumab/epacadostat doublet

9.2.2. Sample Size in Part 2

9.2.2.1. Safety/Efficacy Expansion Cohorts

The safety/efficacy expansion in Part 2 will include 2 cohorts per treatment group, subjects with NSCLC who have had disease progression on a prior PD-1 pathway-targeted agent and subjects with MSS CRC. A Simon 2-stage design will be used for each of the cohorts. The response rates for the historical control (p_0), desired response rates for the combination (p_1), number of subjects needed in Stage 1 (n_1) and Stage 2 (n_2), total number of subjects (n), first stage threshold declaring cohort undesirable (r_1), and the upper limit of the number of responses in n subjects such that futility of the drug is concluded (r) are provided for each expansion cohort in Table 56. The calculation is based on a 1-sided Type I error of 0.05 and power of 80%.

Table 56: Simon 2-Stage Design

Cohort	Tumor Type	Po	Pt	nt	nZ	n	Tt	r
Expansion Cohort A-1	NSCLC subjects who have had disease progression on a prior PD-1 pathway-targeted agent	3%	20%	8	19	27	0	2
Expansion Cohort A-2	MSSCRC	3%	20%	8	19	27	0	2
Expansion Cohort B-7	NSCLC subjects who have had disease progression on a prior PD-1 pathway-targeted agent	3%	20%	8	19	27	0	2
Expansion Cohort B-8	MSSCRC	3%	20%	8	19	27	0	2
Expansion Cohort C-9	NSCLC subjects who have had disease progression on a prior PD-1 pathway-targeted agent	3%	20%	8	19	27	0	2
Expansion Cohort C-10	MSSCRC	3%	20%	8	19	27	0	2

9.2.2.2. Sample Size for Treatment Sequencing Tumor Biopsy Cohorts

Three treatment sequencing tumor biopsy cohorts per treatment group will be emolled to evaluate epigenetic and tumor microenvironment changes. Five to 8 evaluable subjects per each tumor type will be emolled in Expansion Cohorts A-3, A-4, B-9 through B-11, and C-11 through C-13. The eligible tumor types are HNSCC, melanoma, urothelial carcinoma, and MSS CRC. Subjects with tumor types other than MSS CRC must have had disease progression on a prior PD-1 pathway-targeted agent. Ten subjects with first-line melanoma will be emolled in Expansion Cohort A-5. See [Table 5](#), [Table 7](#), and [Table 9](#) for more details regarding treatment sequences and biopsy sequences for Treatment Groups A, B, and C, respectively.

Assuming the true rate of subjects positive for the biomarker is 70%, the probability of observing 16 or more subjects out of 25 subjects with the biomarker is 81% for Expansion Cohorts A-3, A-4, B-9, through B-11, and C-11 through C-13, and the probability of observing 6 or more subjects out of 10 subjects with the biomarker is 85% for Expansion Cohort A-5.

9.3. Level of Significance

For the primary efficacy endpoints, the 1-sided Type I error will be controlled at 0.05 for each individual cohort expansion. For other endpoints, CIs will be reported at a 95% confidence level. Note that this level of significance does not account for the multiple expansion cohorts.

9-4_ Statistical Analyses

9.4.1. Primary Analyses

Part 1: The clinical safety data (vital signs, ECGs, routine laboratory tests, and AEs) for subjects with advanced or metastatic solid tumors will be summarized using descriptive statistics (eg, mean, frequency) using the safety population, which is detailed in Section 9.4.4.

Part 2: The proportion of subjects with previously treated Stage IV or recurrent NSCLC, Stage IV MSS CRC, and other selected solid tumors who meet the objective response criteria (CR + PR), as per RECIST v1.1, will be estimated with 95% CI.

[figure not shown]
9.4.2. Secondary Analyses

Part 1: The proportion of subjects with advanced or metastatic solid tumors who meet the objective response criteria (CR + PR), as per RECIST v1.1, will be estimated with 95% CI.

Part 2: The clinical safety data (vital signs, ECGs, routine laboratory tests, and AEs) for subjects with previously treated Stage IV or recurrent NSCLC, Stage IV MSS CRC, and other select solid tumors will be summarized using descriptive statistics (eg, mean, frequency) using the safety population, which is detailed in Section 9.4.4.

Parts 1 and 2: The percentage of TIL responders for subjects with advanced or metastatic solid tumors and previously treated Stage IV or recurrent NSCLC and Stage IV MSS CRC will be estimated with 95% CI. A subject is considered a TIL responder if the subject has an increase in the number of TILs or the ratio of CD8+ lymphocytes to Tregs infiltrating tumor post-treatment versus pretreatment with pembrolizumab and epacadostat in combination with azacitidine, INCB057643, or INCB059872 evaluated by IHC.

Parts 1 and 2: PFS and DOR of subjects with advanced or metastatic solid tumors and previously treated Stage IV or recurrent NSCLC and Stage IV MSS CRC will be estimated using Kaplan-Meier method as per RECIST v1.1 if there are enough observations.

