In addition to the 6 Simon 2-stage safety/efficacy expansion cohorts, another 9 treatment sequencing tumor biopsy cohorts will be emolled to evaluate epigenetic and tumor microenvironment changes. A total of 25 subjects will be emolled in each Expansion Cohorts A-3, A-4, B-9 through B-11 and C-11 through C-13, and 10 first-line melanoma subjects will be emolled in Expansion Cohort A-5.

In the Part 2 treatment sequencing tumor biopsy cohorts, assuming the true rate of subjects positive for the biomarker is 70%, the probability of observing 16 or more subjects out of 25 subjects with the biomarker is 81% for Expansion Cohorts A-3, A-4, B-9 through B-11, and C-11 through C-13 and the probability of observing 6 or more subjects out of 10 subjects with the biomarker is 85% for Expansion Cohort A-5.

All statistical analyses are descriptive in nature. Descriptive statistics will be deduced where appropriate. Continuous endpoints will be summarized with number of subjects, mean, standard deviation, minimum, median, and maximum for each cohort. Categorical endpoints will be summarized with frequency and percent for each cohort.

If data warrants, ORR will be estimated with 95% exact confidence interval. Time to event endpoints such as DOR, PFS, and OS will be summarized with Kaplan-Meier estimates by cohort.

TABLE OF CONTENTS

SYNOPSIS	3
LIST OF ABBREVIATIONS.....	31
1. INTRODUCTION	36
1.1. Innunotherapy in Cancer	36
1.2. Overview of Pembrolizumab.....	38
1.3. Overview of Epacadostat.....	38
1.4. Overview of Azacitidine.....	40
1.5. Overview of iNCB057643.....	41
1.6. Overview of iNCB059872.....	44
1.7. Study Rationale.....	46
1.7.1. Rationale for Combining Epigenetic Therapy With Innunotherapy	46
1.7.2. Justification for the Treatment Regimen	48
1.7.3. Rationale for Phase 2 Subject Populations	52
1.7.3.1. Non-Small Cell Lung Cancer.....	52
1.7.3.2. Microsatellite Stable Colorectal Cancer	54
1.7.3.3. Treatment Sequencing Tumor Biopsy Cohort Indications	55
1.8. Potential Risks and Benefits of the Treatment Regimen	55
■ [REDACTED]	55
1.8.2. Risks From Pembrolizumab	57
1.8.3. Risks From Azacitidine	57
1.8.4. Risks From INCB057643	57
1.8.5. Risks From INCB059872	58
1.8.6. Risks From Combination Therapy.....	58
2. STUDY OBJECTIVES AND ENDPOINTS.....	59
2.1. Study Objectives.....	59
2.1.1. Primary Objectives	59
2.1.2. Secondary Objectives	59
■ [REDACTED]	59
2.2. Study Endpoints.....	60
2.2.1. Primary Endpoints	60
2.2.2. Secondary Endpoints	60

		61

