2.2.2. Secondary Endpoints

- Pa1t 1: Objective response rate, defined as the percentage of subjects having a CR or PR, will be detelmined by investigator assessment of radiographic disease as per RECIST v1.1.
- Pa1t2: Safety and tolerability will be assessed by monitoring the frequency, duration, and severity of AEs; through physical examinations; by evaluating changes in vital signs and ECGs; and through clinicallaboratmy blood and urine sample evaluations.
- Pa1ts 1 and 2: Percentage of responders, where a responder is defined as an increase in the number of TILs or the ratio of CD8+ lymphocytes to Tregs infiltrating tumor post-treatment versus pretreatment with pembrolizumab and epacadostat in combination with azacitidine, INCB057643, or INCB059872 evaluated by IHC, will be detelmined.
- Pa1ts 1 and 2: Progression-free smvival, defmed as the time from date of first dose of study dmg until the earliest date of disease progression, will be detelmined by investigator assessment of objective radiographic disease assessments per RECIST v1.1, or death due to any cause, if occmTing sooner than progression.
- Pa1ts 1 and 2: Duration of response detelmined by radiographic disease assessment, defined as the time from earliest date of disease response until the earliest date of disease progression as per RECIST v1.1, or death due to any cause, if occmTing sooner than progression, will be detelmined.

3_ SUBJECT ELIGIBILITY

Deviations from eligibility criteria are not allowed because they can potentially jeopardize the scientific integrity of the study, regulatory acceptability, and/or subject safety. Therefore, adherence to the criteria as specified in the Protocol is essential.

3-L Subject Inclusion Criteria

A subject who meets all of the following criteria may be included in the study:

Both Part 1 and 2

1. Male or female subjects, age 18 years or older on day of signing consent.
2. Willingness to provide written informed consent for the study.
3. Willingness to undergo a pretreatment and on-treatment tumor biopsy to obtain tumor tissue. On-treatment biopsy is optional in Stage 2 of Part 2. Two on-treatment biopsies are mandatory in the Part 2 treatment sequencing biopsy expansion cohorts (except for Cohorts B-11 and C-13, which require 1 on-treatment biopsy).

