Part 2 of the study will be an open-label Phase 2 assessment with Simon 2-stage design to evaluate ORR and TIL infiltration in previously treated NSCLC and MSS CRC. Separate treatment sequencing tumor biopsy cohorts are also included in Part 2 to further evaluate epigenetic changes and changes in the tumor microenvironment in subjects with select solid tumors.

Tumor biopsy samples are required at baseline and on study for subject participation in all dose-escalation cohorts and Stage 1 of the Simon 2-stage cohorts. Mandatory tumor biopsies will be collected at baseline (before Day 1 administration) and while the subject is receiving study treatment as specified below:

- An additional on-treatment biopsy will be required to be collected during Week 5 or Week 6 (Treatment Group A) or Week 8 or Week 9 (Treatment Groups B and C); the on-treatment biopsy is optional for Stage 2 cohorts in Part 2. On-treatment biopsy requirements for the treatment sequencing biopsy cohorts are presented in [Table 5](#), [Table 7](#), and [Table 9](#).
- An additional optional biopsy may be collected once the subject meets the requirements for SD, response, or progression by radiographic disease assessment.

Note: On-treatment biopsies should be collected from the same tumor lesion that was biopsied at baseline.

Note: If a subject is scheduled to have a tumor biopsy for the purposes of this study, and it is subsequently determined that tumor tissue cannot safely be obtained, then the subject may still enroll in the study, and an archived tumor specimen, if available, can be submitted. Such subjects may be replaced.

Note: As a quality control step, prior to submitting the tumor tissue to the central laboratory vendor, all tumor tissue will be formalin-fixed and paraffin-embedded locally. A hematoxylin and eosin (H&E) stain will be performed and reviewed by a local pathologist to verify the adequacy of the tumor biopsy. Additionally, a quality control form will be signed and dated by the reviewing pathologist. For the screening biopsy, this form will ideally be submitted to the sponsor at the same time that the registration form is submitted for enrollment.

[REDACTED]
Toxicities will be monitored continuously and will be graded by the NCI CTCAE v4.03.

Treatment Group A

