5.2. Treatment Groups

This is an open-label, multicenter, Phase 1/2 study evaluating the addition of an epigenetic priming regimen to an immunotherapy doublet in subjects with advanced or metastatic solid tumors. The study will be conducted in 2 parts.

Due to the stop of study enrollment, only subjects in Treatment Group A have been enrolled into Parts 1 and 2. Data from Parts 1 and 2 for Treatment Group A will be summarized together by dose level. The dose levels for Treatment Group A are shown in [Table 1](#).

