7.1. General Considerations

Efficacy endpoints of this study include ORR, DOR, PFS and OS by investigator assessment based on RECIST v1.1. Listings of response assessment at each visit will be provided.

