10.1.3. Interim Analyses

- Simon 2-stage design will not be performed due to the early termination of the study. No interim analyses will be conducted for Part 2.

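### In the readable text, the secondary TIL response rate counts any rise in either of two measures with no reference rate, so a moderate percentage cannot by itself be read as immune activation

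*Protocol*

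**What the plan says.** Change in T-cell infiltration is a secondary objective for both parts (Protocol 2.1.2, SAP 2.2.2). The endpoint attached to it, in Protocol 2.2.2 and again in SAP 2.3.2, is a percentage of responders, where "a responder is defined as an increase in the number of TILs or the ratio of CD8+ lymphocytes to Tregs". Protocol 9.4.2 turns this into the analysis rule: a patient responds if "the subject has an increase in the number of TILs or the ratio of CD8+ lymphocytes to Tregs infiltrating tumor post-treatment versus pretreatment", judged by immunohistochemistry. The percentage is to be estimated with a 95% CI.

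Protocol 9.3 adds only that "For other endpoints, CIs will be reported at a 95% confidence level". The Synopsis, under Statistical Methods, says that "All statistical analyses are descriptive in nature" and calls the study nonrandomized. The readable text contains no minimum change, no rate expected without an effect, and no untreated paired-biopsy group.

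Several rules limit biopsy variation. Baseline and on-treatment samples should come from the same lesion, and a local pathologist confirms adequacy and signs a form (Protocol 4.1 and 7.6.2). Fine-needle aspirates are not accepted (Protocol Table 29).

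On how many pairs there will be, Protocol 4.1 says that "the on-treatment biopsy is optional for Stage 2 cohorts in Part 2". SAP 10.1.3 says that "Simon 2-stage design will not be performed due to the early termination of the study".

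**The concern.** An any-increase rule makes an unchanged tumor a response whenever the second biopsy happens to read higher than the first. Accepting either of two measures gives chance a second opportunity. The rate expected with no treatment effect is therefore well above zero, and the documents do not let a reader work out what it is.

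The 95% CI shows how precisely the percentage is estimated. It does not show how much of that percentage would have appeared anyway. At stake is the reading of a stated secondary objective: a rate such as 65% or 70% could be reported as evidence of immune activation when biopsy noise alone could produce it.

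**Working it through.** **The plan's own figures.** None is given for the TIL endpoint. The nearest is in Protocol 9.2.2.2 and SAP 3.4.2.2, for the sequencing biopsy cohorts. With an assumed true biomarker rate of 70%, the chance of 16 or more of 25 is 81%, and of 6 or more of 10 is 85%. Exact binomial tails give 0.8106 and 0.8497, so both reproduce. That 70% is an assumed true rate for an unnamed biomarker. It is not a no-effect rate and is not tied to TIL.

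**Inputs for the no-effect rate.** The either/or rule with no threshold comes from Protocol 9.4.2. The within-pair variability, the correlation ρ between the two changes and the share of ties are not in the documents. I assume symmetric bivariate-normal changes and vary ρ and the tie share.

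**Untied case.** One measure rises in 50% of unchanged tumors. Both fall with probability 1/4 + arcsin(ρ)/(2π), so at least one rises with probability 3/4 − arcsin(ρ)/(2π).

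| ρ | Either/or rate with no effect |
|---|---|
| 1 | 0.75 − 0.25 = 50% |
| 0.9 | 57% |
| 0.5 | 0.75 − 1/12 = 67% |
| 0.3 | 70% |
| 0 | 75% |

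A negative correlation would push the rate above 75% (83% at ρ = −0.5). The documents give no basis for assuming or excluding one.

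**Ties.** If a share t of pairs is tied on each measure, one measure rises in s = (1 − t)/2. With ρ = 0 the either/or rate is 1 − (1 − s)².

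- t = 10%: s = 0.45, rate 1 − 0.55² = 69.8%
- t = 20%: s = 0.40, rate 1 − 0.60² = 64%

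At ρ = 0.5 the rates are 62% and 56%; at ρ = 1 they are 45% and 40%.

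**What the CI can show.** Protocol 9.4.2 names no CI method, so I use exact (Clopper-Pearson) limits. Eight is the planned Stage 1 size, where the on-treatment biopsy is mandatory. It serves only as an illustration, since the actual number of pairs is unknown.

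- 6 of 8 is 75%, with limits 34.9% to 96.8%, which span the whole 50% to 75% range.
- 8 of 8 has a lower limit of 63.1%, above 50% but below 66.7% and 75%. Noise alone gives 8 of 8 with probability 0.5⁸ = 0.004, 0.667⁸ = 0.039 or 0.75⁸ = 0.100.
- When all n pairs respond, the lower limit is 0.025^(1/n). It exceeds 75% only if n > ln(0.025)/ln(0.75) = 3.689/0.2877 = 12.8, so at least 13 pairs are needed even if every one is a response.

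**The case against.** The strongest reply has four parts.

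**The endpoint is secondary and descriptive.** No visible decision rule uses it, and enrollment has stopped with only Treatment Group A enrolled. All of this stands and keeps the point at the level of a cheap improvement.

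**The missing analysis may be behind redactions.** Protocol 9.4.3, SAP 10.1.2, a SAP contents entry just after 7.2.5 and an efficacy row in SAP Appendix A cannot be read. This also stands, and the fix is conditional on it. A reader might infer that the SAP dropped the TIL analysis, because SAP 7.1 says "Efficacy endpoints of this study include ORR, DOR, PFS and OS by investigator assessment based on RECIST v1.1". The documents do not support that: the sentence concerns RECIST-based endpoints, SAP 2.3.2 keeps the TIL endpoint, and a redacted section may analyze it. What does not depend on the redactions is the visible rule itself.

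**The safeguards limit noise.** They do, so it would be wrong to say the plan ignores biopsy variation. But none of them yields a no-effect rate.

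**The 50% to 75% range is assumed, and a very high rate would exceed it.** Correct on both counts. A reader might infer that no TIL result could be informative; under these assumptions a lower limit above about 75% would be. A reader might also infer that noise would satisfy the 16-of-25 benchmark. The documents do not name TIL as that biomarker, so this does not follow.

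**Conclusion.** The point holds in a limited form. Followed exactly, the visible rule would produce a substantial responder rate with no treatment effect. That rate is about 50% to 75% if residual noise is symmetric, untied and not negatively correlated between the two measures. With 10% or 20% ties and independent measures, the top of the range falls to about 70% or 64%. The true value is unknown because none of these inputs is documented, so the range is an illustration and not an estimate of a false-positive rate in this trial.

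A moderate TIL response rate cannot by itself be read as immune activation. The primary endpoint and the design are unaffected.

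**What to change.** Keep the Protocol-defined rate. Unless a redacted section already does this, add the following to the SAP for TIL number and for CD8+/Treg ratio separately, and record it in SAP 10.1:

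1. The paired on-treatment versus baseline change with a 95% CI, for example as a log-ratio, or as a median paired difference where zeros occur. State in advance how zero counts are handled, including zero Tregs, where the ratio is undefined.
2. The number of evaluable pairs and the counts of increases, decreases and ties. Compare increases with decreases descriptively among untied pairs, where symmetric noise gives a 50% reference whatever the correlation between measures. Do not set the all-patient rate against 50%, since ties lower its no-effect value to 45% or 40% (at 10% or 20% ties).

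This deals with symmetric biopsy noise and the either/or inflation. It does not supply a control and would not remove a systematic shift between the two biopsies. With very few pairs it says little: with five untied pairs, all increasing, the two-sided sign-test p-value is 2 × 0.5⁵ = 0.0625.

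The biopsies and staining data are those already collected. The cost is a short SAP paragraph, one or two tables, a zero-count rule to agree beforehand, and per-measure percentages that will look less favorable than the combined rate.
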